4.5.7 Genetic Profiling

The blood and endothelial specimens will be analyzed upon completion of the study for RNA, microRNA, and DNA profiling. We will perform detailed molecular profile study, describing genetic arrays of patterns of platelet and endothelial vein analysis associated with atherosclerotic heart disease and psoriasis. We will be looking at specific transcripts in various cell types and endothelial cells associated with cardiovascular diseases. Platelet-rich plasma (PRP) will be isolated for platelet purification and subsequent genetic analysis will be performed. The samples will be stored in dedicated freezer space in the Marc and Ruti Bell Program for Vascular Biology (the NYU Science building 7th floor) for the PI without any identifying information other than a unique code number. The code number will not be based on any information that could be used to identify the subject (for example, social security number, initials, birth date, etc.). The master list linking names to code numbers will be kept in a locked file cabinet, separate from all research information. Genetic information will not be disclosed to anyone, including the participants and their physicians. Samples shall be destroyed at the end of the testing process.

4.6 Future Sample Storage

All patients will be offered an option to have their blood stored for future processing. If patient does not agree to store his/her blood for future tests not related to this study, then his/her blood will be destroyed after all planned laboratory tests have been performed.

Blood samples for future analysis will be assigned a unique code number and stored in the dedicated freezer storage by the PI without any identifying information other than a code number. The unique code number will not be based on any information that could be used to identify the subject (for example, social security number, initials, or birth date). The master list linking names to code numbers will be kept in a locked file cabinet, separate from all research information placed under double lock and key at PI's office. All confidential data will be stored with a unique code as an identifier and will be protected by a double electronic lock. All physical data will be kept under double physical lock. Access to the data will be given to the study personnel only.

Samples will be stored for no more than 10 years. The specimens for future analysis may be analyzed upon completion of the study for RNA, microRNA, and DNA as described above. Genetic information will not be disclosed to anyone, including the participants. Samples could also be used for testing other potential biomarkers in patient plasma and/or serum related to psoriatic disease and CVD that may occur with exception of those which are already part of the protocol. Results of the future research will not be shared with the subjects or their study doctor, and will not become part of the medical records.

In the future, other institutions or future collaborators at or outside of NYU Medical Center may want to study a portion of these samples, too. If that happens, samples would be sent to other places so other people interested in studying these diseases and conditions could do that. The samples sent to other researchers will be de-identified without PHI. Samples will be stored for no more than 10 years following completion of the study. At the end of the 10-year period, all samples will be destroyed.

Subjects can request for withdrawal of samples at any time by contacting PI [name] in writing. His mailing address is [name]. Withdrawing Authorization only affects uses and sharing of information after written request has been received, and subject may not withdraw his/her Authorization for uses or disclosures that have previously been made or must continue to complete analyses or report data from the research.

5. RISKS

The potential risks of phlebotomy are pain, bruising, fainting, or small infection at puncture site. The procedure to perform endothelial vein harvesting is identically to the placement of an IV and routine phlebotomy blood draw. These risks are pain, bruising, fainting or small infection at the puncture site.

Sterile gloves and sterile wires are used to harvest the endothelial cells. The wires are advanced < 5 inches. Our lab is partnering with a lab experienced with this technique and has published extensively on the technique for many years¹⁴. In their experience patients complain only on the routine discomfort of the IV insertion. There is a theoretical risk of vein thrombosis. In our collaborators experience, in over 10 years of sampling, not one thrombosis has occurred. To minimize this risk, we will encourage arm mobilization post procedure. We will be using our collaborators protocols and their consent language to ensure adequate patient knowledge on the risks of the procedure and we will train extensively prior to carrying out this low risk minimally invasive procedure to harvest endothelial veins. There lab has also agreed to help mentor and guide us to help with the appropriate and safe procurement of endothelial cells when performing this testing on our initial subject cohort.

Regarding non-invasive imaging of vascular function, there are no known risks associated with taking ultrasound pictures. The cuff on the forearm and the "pins and needles" sensation may be uncomfortable for participants. At their request, the cuff will be deflated and any discomfort should disappear within a few seconds. There are no known risks to the arterial tonometry measurements.

Treatment risks:

Aspirin and atorvastatin are standard medications used for the primary prevention of CVD. Nevertheless, there are risks associated with being on aspirin for 2 weeks. Use of aspirin has known side effects, including stomach irritation, ulcers, heartburn, easy bruising, and minor or major bleeding. Thus, we are using the lowest clinically effective dose (81mg) and for a very short period of time.

There is also a risk of being on 40mg of atorvastatin. There are known side effects to short term therapy which includes hepatotoxicity, myositis, muscle soreness, stomach irritation and interaction with other medications (such as antifungals) and foods (such as grapefruit). We are using a statin (40mg of atorvastatin) which has been widely studied with a low rate of interactions, hepatotoxicity and incidence of myositis.

Genetic risks:

Genetic testing can generate information about a subjects' personal health risks and can cause or increase anxiety, damage family relationships, and/or compromise insurability, employability and can even lead to discrimination. In general, results from studies that use data collected as part of this research will be preliminary, and the clinical implications of any findings may not be understood for years. Therefore, individual study results will not be shared with participants or their physicians.

Potential loss of confidentiality: Confidentiality will be preserved to the fullest extent by the research team but absolute confidentiality can't be guaranteed. All data will be stored with a unique code that does not identify the participant. Furthermore, data will be saved using a double electronic lock. All physical data will also be kept under double physical lock. Access to the data will be given to the study personnel only thereby greatly reducing the possibility of psychological or social risks that could arise from knowledge of this genetic information, such as risk for employability or insurability or the risk of discrimination.

6. BENEFITS

The proposed study will examine the relationships between psoriatic disease, endothelial and vascular function and markers of thrombotic and CVD risk. Further, we will examine how treatment with aspirin and/or statin will improve markers of inflammation and vascular function in those with psoriatic disease. The long-term goal is to develop a better understanding of the role endothelial function and thrombotic risk in those with psoriatic disease. Furthermore we hope to understand the use of accepted primary prevention CVD medications in those that show an elevated risk of CVD through chronic inflammation. This will lead to improved personalized medicine. There may be no direct benefit to enrolled subjects.

7. Cost

There is no cost to the study participants. There is also no direct benefit expected from the participation in this study. This study may provide valuable information to medical/cardiovascular physician scientist's with minimal risk to study subjects. It is hoped that knowledge gained will be of benefit to others in the future.

8. Reimbursement:

Both control subjects and psoriasis subjects may be reimbursed up to 100 dollars.

9. STATISTICAL ANALYSIS

This is a pilot study designed to investigate a novel technique of endothelial vein sampling, vascular function, and assessment of thrombotic risk in a population that is under studied.

In the first publication of this endothelial vein harvesting technique comparing subjects with and without severe decompensated heart failure, an $n = 5$ per group showed differences in markers of endothelial dysfunction.¹⁵ There is data on imaging techniques to assess endothelial dysfunction in psoriatic disease. For non-invasive vascular imaging techniques, previous studies have shown upwards of a 35% difference in measurements of endothelial dysfunction between those with psoriasis and healthy controls.¹⁶

Specific Power Analysis:

Based on the above study evaluating endothelial dysfunction in psoriatic patients, we have a power > 80% with an alpha level of 0.05 to detect a 35% difference using non-invasive vascular imaging in those with psoriatic disease compared to healthy controls with a goal $n = 40$ for the psoriatic group and $n = 10$ for the control group (G*Power 3.1.9.2). We do not have comparable data on the use of endothelial harvesting techniques to compare psoriatic disease to healthy controls. In previous studies using endothelial harvesting to study heart failure, staining for NF-kB (non-specific marker of inflammation and endothelial dysfunction) yielded a 16% difference between groups, a narrow standard deviation with an effect size d of 1.2. Extrapolating this measurement with an $n = 40$ for psoriatic disease and $n = 10$ for controls gives us > 90% power to detect baseline endothelial function differences between groups with an alpha level of 0.05 (G*Power 3.1.9.2). For the longitudinal component assessing endothelial function with endothelial vein harvesting and staining for NF-kB, $n = 10$ per group and pre and post aspirin/atorvastatin and assuming an effect size d of 0.8¹⁷, we would have a 74% power with an alpha level of 0.05 to detect a difference between groups (G*Power 3.1.9.2). We believe given the pilot nature of this study, the sample sizes are adequate to detect both cross sectional and longitudinal trends which would then allow for further study proposals.

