4.5.2 Longitudinal component (Group 1 only)

After baseline assessment, those with moderate to severe psoriatic disease will be offered by the study physician randomly the opportunity for longitudinal follow up and to take either aspirin and/or atorvastatin. For 2 weeks +/- 4 days, 1/4th of the subjects enrolled will be offered 81mg of aspirin, 1/4th of the subjects enrolled will be offered atorvastatin 40mg, ¼ will be offered both aspirin and atorvastatin and 1/4th will be offered nothing. Participants will be given the opportunity to only participate in the baseline assessment and opt out of the opportunity to take aspirin and/or atorvastatin and longitudinal component.

Both aspirin and atorvastatin are routinely used and approved in medical practice for the primary prevention of coronary artery disease. These medications are frequently used in the psoriatic population based on national guidelines when a calculated cardiac risk score is elevated (considered at moderate to high risk of cardiovascular events). These medications will be obtained from the Tisch outpatient pharmacy. They will be stored and dispensed with CTSI oversight. A drug accountability and storage log will be kept as per NYU research protocol.

A follow up assessment will be planed (table 1) at 2 weeks +/- 4 days and will include repeat blood draw (60 ccs, for the use of platelet function testing, biospecimen collection) and repeated endothelial vein harvesting. The end of the study is considered when the subject completes the follow up assessment. All study drugs will be stopped at this time. If the subject wishes to continue the study drugs they will be referred to their primary medical provider for further management.

A subject will be able to opt out of any part of the follow up assessment they desire. If a subject agrees to be started on aspirin and/or atorvastatin for the longitudinal part of the analysis and therapy for psoriasis is planned by the referring provider, we will attempt to perform the longitudinal follow up prior to their starting medication. Participation in this study will not impact planned treatment of the subjects by their primary provider.

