We will evaluate the association between moderate to severe psoriatic disease and measures of thrombotic risk. As in Aim1, linear and nonlinear regression models will be employed to investigate the difference in platelet activity between those with and without psoriasis. This is gauged by monocyte platelet activity (MPA) and assessing monocyte – platelet interaction after adjusting for other covariates and applying model selection procedures. We will collect data including maximal aggregation (%), slope of the aggregation curve, and elapsed time between addition of agonist and onset of aggregation (lag phase). Regression models will unveil how these characteristics are influenced by those exposed to psoriatic disease, adjusting for other covariates.

c. Aim 3

We will then investigate how traditional medications used in CVD prevention such as aspirin and statins affect vascular function and thrombotic risk in those with moderate to severe psoriatic disease. We will assess baseline endothelial vein transcriptome data, genetic expression for routine markers of endothelial activation such as VCAM-1, ICAM-1, NF-kB and platelet reactivity data. Using paired t- tests, we will assess the changes to platelet reactivity and endothelial function with the use of aspirin, aspirin plus atorvastatin or atorvastatin therapy.

11. Safety and Adverse Events

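### The 74% longitudinal power is labelled as between groups, but 10 v 10 at d = 0.8 gives 40% two-sided, and the planned within-arm paired t-test gives 62%

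*Combined protocol and SAP*

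**What the plan says.** Section 9 (Statistical Analysis, Specific Power Analysis) takes 10 subjects per group measured before and after aspirin/atorvastatin, an effect size d of 0.8 and alpha 0.05. It concludes that "we would have a 74% power with an alpha level of 0.05 to detect a difference between groups". The next sentence calls the sample sizes adequate, for a pilot, to detect cross-sectional and longitudinal trends.

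Section 10 (Data Analysis, Aim 3) gives the analysis: "Using paired t- tests, we will assess the changes to platelet reactivity and endothelial function" under aspirin, atorvastatin or both. It describes no arm-versus-arm test.

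Section 4.5.2 splits the psoriatic group into quarters ("1/4th of the subjects enrolled will be offered 81mg of aspirin", with the other quarters offered atorvastatin, both drugs or nothing). It also says "Participants will be given the opportunity to only participate in the baseline assessment and opt out" of the drug and longitudinal component, and "A subject will be able to opt out of any part of the follow up assessment they desire".

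Neither section 9 nor section 10 states whether the test is one- or two-sided, what kind of d is meant, or a pre/post correlation for NF-kB staining.

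**The concern.** The power sentence describes a pre/post design but ends by claiming power for a difference between groups. In the sentence just before it in section 9, the same phrase means patients against controls, that is, separate people. A reader will take it the same way here and conclude that the trial has 74% power to separate one arm from another. No such test is planned, and 10 per arm looks too few for that power at d = 0.8.

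This is the only power figure for Aim 3, the aim under which study drug is given, and the statement of adequacy rests on it. Read at face value, the chance of missing d = 0.8 is 26%. If the true chance is larger, a null result could be over-read as absence of effect, and a follow-on study could be planned from an optimistic figure.

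**Working it through.** **Inputs.** From section 9: n = 10 per group, d = 0.8, alpha 0.05, stated power 74%. From sections 4.5.1–4.5.2 and Table 1: 40 patients in four quarters, so 40/4 = 10 per arm. From section 10: a paired t-test for each regimen. Sidedness, type of d and pre/post correlation are not given, so both tails are tried and d is first taken as the standardised difference or change in the quantity compared.

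**Method.** Exact noncentral t, where power is the probability that a noncentral t with noncentrality δ falls beyond the critical value.
- Paired: df = n − 1, δ = d√n. With n = 10: df = 9, δ = 0.8 × √10 = 2.53. Critical values: 1.833 one-sided, 2.262 two-sided.
- Two groups of 10: df = 18, δ = d√(n/2) = 0.8 × √5 = 1.79. Critical values: 1.734 one-sided, 2.101 two-sided.

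**Trying to reproduce 74%.**

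| Test at d = 0.8 | Two-sided | One-sided |
|---|---|---|
| 10 v 10, between groups | 39.5% | 53.0% |
| 10 pairs, paired t | 61.6% | 75.4% |
| 10 pairs, signed-rank approximation (n × 3/π ≈ 9.55) | 59.1% | 73.4% |

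Only the one-sided within-arm rows come within about two points of 74%. The between-group row does not, under either tail.

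**Does the baseline power figure settle the sidedness?** No. For 40 v 10 at d = 1.2, δ = 1.2 × √(40 × 10/50) = 3.39 with df = 48. That gives 91.4% two-sided and 95.6% one-sided. Section 9 states more than 90%, which fits both.

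**What 74% would need, two-sided.**
- With n = 10: a standardised change of 0.925 (paired), or d = 1.23 (10 v 10).
- With d = 0.8: 13 pairs, or 23 per arm.

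**If d is in raw-score SD units.** With pre/post correlation ρ (an assumption) and equal variances, the standardised change is 0.8/√(2(1 − ρ)). Two-sided power is then:

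| ρ | Standardised change | 10 pairs | Change scores, 10 v 10 |
|---|---|---|---|
| 0.3 | 0.676 | 48% | 30% |
| 0.5 | 0.800 | 62% | 40% |
| 0.7 | 1.033 | 83% | 59% |
| 0.8 | 1.265 | 94% | 76% |

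Two-sided 74% is reached at ρ of about 0.63 (paired) or 0.79 (10 v 10).

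**Fewer pairs.** Two-sided paired power at a standardised change of 0.8 is 55.9% with 9 pairs and 49.6% with 8. The numbers 9 and 8 are illustrations.

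**The case against.** The best defence is that nothing was miscalculated. The sentence itself mentions pre and post, section 10 plans paired tests, and a one-sided paired t-test with 10 pairs gives 75.4%. On that reading the stated 74% is slightly conservative and the last phrase is loose wording. Section 6 expects treatment to improve the markers, which is compatible with a one-sided test. If d is on the raw scale, a correlation of about 0.63 makes 74% right for the planned test, two-sided. A three-arm repeated-measures F test with f = 0.4 and zero correlation also gives 74.9%. And this is a pilot that already reports power below 80% and claims only to detect trends.

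Much of this stands. The number probably comes from a one-sided within-arm calculation, so the fault lies in the label and the undeclared assumptions rather than in the computation. The 62% depends on a two-sided test and on d being a standardised change. The 40% and 53% concern a comparison that the plan does not make; they matter because the sentence claims power for it.

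It does not rescue the sentence. Each route to 74% needs something the plan does not state: a one-sided test, a correlation, or an effect size f with an F test that is not planned. A directional expectation does not declare a one-sided test. Pilot status excuses low power, but not a stated power that belongs to a different test.

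**Conclusion.** The concern holds. From the stated inputs, 74% is not the power of a between-group comparison under either tail (39.5% or 53.0%), nor of the planned paired t-test at the conventional two-sided 0.05 (61.6%). For that planned test, the chance of missing a standardised change of 0.8 is 38% rather than the implied 26%, and 44% if one patient per arm is lost.

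The between-group result and the absence of a declared sidedness are firm. The 62% rests on two assumptions: a two-sided test, and d as the standardised within-patient change. If a one-sided test was intended, the power is about 75% and the error is confined to the label and the missing declaration. If d is on the raw scale, the power depends on a correlation that the plan does not give. The point should be fixed because the statement of adequacy depends on the figure, but it does not invalidate the design.

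**What to change.** Replace the sentence in section 9 with the power of the Aim 3 test, naming the test, the sidedness and the type of d. If a two-sided test and a standardised change are meant, for example:

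> *With 10 pairs per regimen, a two-sided paired t-test at alpha 0.05 has about 62% power for a standardised within-patient change of 0.8; 74% power would need a standardised change of about 0.92. Ten pairs assumes that every patient joins and completes follow-up; with 9 pairs the power is about 56%.*

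Delete the reference to a difference between groups, or add that a 10 v 10 comparison at d = 0.8 has about 40% power two-sided. If a one-sided test was intended, declare it in sections 9 and 10. If d is in raw-score units, say so and give the assumed pre/post correlation and its basis.

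The cost is a text edit and probably a less favourable figure. No patients, visits or analyses are added.

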10. DATA ANALYSIS

All eligible subjects will be assigned a unique identification number upon enrollment in the study. Initial study data will be recorded on a printed form, which will be later converted to electronic database (Redcap). All potential identifiers will be kept separately in a safe location by the PI in a locked file cabinet in a locked room. After verification of entered data at completion of the study all potential identifiers will be stripped from the database.

a. Aim 1

To evaluate the association between moderate to severe psoriatic disease and measures of vascular function. Brachial artery reactivity will be modeled as a continuous variable in all analyses. Multiple linear regression will be used to estimate the difference in brachial artery reactivity between those with psoriasis and age and sex matched controls. Conventional adjustment for age and sex will be entered first into the model. Additional multivariable adjustment for other relevant covariates (e.g., body mass index, hypertension, renal function, LDL cholesterol) will then be performed.

A similar analysis plan will be undertaken for central pulse pressure (CPP) and pulse wave velocity (PWV) which will be modeled as continuous variables in all analyses. Multiple linear regression will be used to estimate the difference in CPP and PWV between those with psoriasis and age and sex matched controls. Conventional adjustment for age and sex will be entered first into the model. Additional multivariable adjustment for other relevant covariates (e.g., body mass index, hypertension, renal function, and LDL cholesterol) will then be performed.

For endothelial vein analysis quantitative Immunofluorescence will be performed. The human endothelial cells will be identified by staining with polyclonal rabbit antihuman VE Cadherin antibodies (Abcam), followed by secondary biotin-conjugated donkey antirabbit antibodies (Jackson ImmunoResearch Laboratories) preconjugated with Streptavidin oregon green (Molecular Probes). Nuclear NFkB (fluorescence intensity) and expression of MCP-1, ICAM-1, VCAM-1, iNOS, COX-2, eNOS, P-eNOS will be assed. Negative control slides will be generated by using preimmune mouse IgG (Sigma Chemical) as primary antibodies. Immunofluorescence analysis will be performed in a blinded fashion by numerically coding each slide. Staining will be visualized with ultraviolet light under a fluorescent microscope (Nikon ECLIPSE E600, Melville, NY) using a COHU charge coupled device camera (Danville, CA). Image processing will be performed by using ImageJ and expressed as fluorescence area in μm^2 . Slides will be systematically read left to right and top to bottom. Only cells with both cellular and nuclear integrity will be analyzed. Cellular and nuclear integrity will be assessed morphologically. Intact cells will be defined as those with continuous, unbroken cell membrane delineated by VE Cadherine staining, as analyzed by phase contrast microscopy. Intact nuclei will be defined as well-circumscribed oval bodies as delineated by DAPI staining.

Additionally, real-time quantitative RT-PCR will be performed. One microgram of total RNA will be reverse-transcribed to cDNA with Superscript II reverse transcriptase and poly dT priming according to the manufacturer's instruction (Life Technologies). Real-time quantitative PCRs will be performed with a LightCycler thermal cycler (Idaho Technology, Salt Lake City, UT) as previously described.⁴⁰ We will assess mRNA expression of MCP-1, ICAM-1, VCAM-1, iNOS, COX-2, eNOS (fold change over healthy controls). Untargeted RNA-sequencing will also be performed for untargeted analysis to identify novel markers of psoriatic disease and activity.

b. Aim 2

We will evaluate the association between moderate to severe psoriatic disease and measures of thrombotic risk. As in Aim1, linear and nonlinear regression models will be employed to investigate the difference in platelet activity between those with and without psoriasis. This is gauged by monocyte platelet activity (MPA) and assessing monocyte – platelet interaction after adjusting for other covariates and applying model selection procedures. We will collect data including maximal aggregation (%), slope of the aggregation curve, and elapsed time between addition of agonist and onset of aggregation (lag phase). Regression models will unveil how these characteristics are influenced by those exposed to psoriatic disease, adjusting for other covariates.

c. Aim 3

We will then investigate how traditional medications used in CVD prevention such as aspirin and statins affect vascular function and thrombotic risk in those with moderate to severe psoriatic disease. We will assess baseline endothelial vein transcriptome data, genetic expression for routine markers of endothelial activation such as VCAM-1, ICAM-1, NF-kB and platelet reactivity data. Using paired t- tests, we will assess the changes to platelet reactivity and endothelial function with the use of aspirin, aspirin plus atorvastatin or atorvastatin therapy.

11. Safety and Adverse Events

